9.12.6 C-SSRS

C-SSRS will be summarized for each cohort and cohort total, and baseline for Cohort 1 is defined as baseline at DSP-5423(tablet) treatment period and one for Cohort 2 is defined as baseline at DSP-5423P application period.

For ‘Suicidal ideation’, the number and percentage of subjects by items, with any suicidal ideation, with no suicidal ideation, with serious suicidal ideation defined as ‘Yes’ in item 4 or item 5, will be summarized at baseline, each visit, entire DSP-5423(tablet) treatment period, and entire DSP-5423P application period.

Suicidal ideation

1. Wish to be dead
2. Non-specific active suicidal thoughts
3. Active suicidal ideation with any methods [not plan] without intent to act
4. Active suicidal ideation with some intent to act, without specific plan
5. Active suicidal ideation with specific plan and intent

For ‘Suicidal behavior’, the number and percentage of subjects by items, with any suicidal behavior, and with no suicidal behavior will be summarized at baseline, each visit, entire DSP-5423(tablet) treatment period, and entire DSP-5423P application period.

Suicidal behavior

1. Any actual attempts

2. Any interrupted attempts
3. Any aborted attempts
4. Any preparatory acts or behavior

The number and percentage of subjects with either suicidal ideation or suicidal behavior as ‘any suicidality’, and with no suicidality will be summarized at baseline, each visit, entire DSP-5423(tablet) treatment period, and entire DSP-5423P application period.

The subjects* with ‘emergence of suicidal ideation’ defined as subjects without suicidal ideation at baseline, but not in post-baseline of DSP-5423P application period, subjects* with ‘serious emergence of suicidal ideation’ defined as subjects with ‘No’ in both item 4 and item 5**, but not in post-baseline of DSP-5423P application period, subjects* with ‘emergence of suicidal behavior’ defined as subjects with no suicidal behavior at baseline, but not in post-baseline of DSP-5423P application period, subjects* with “emergence of suicidality” defined as subjects with neither suicidal ideation nor suicidal behavior, but either/both in post-baseline of DSP-5423P application period, subjects with ‘any completed suicide’, will be summarized based on the number and percentages.

* Subject with ‘Yes’ at baseline are not included in the denominator of percentages.

** If item 2 of suicidal ideation is ‘No’, and item 3, 4, and 5 are null, item 3, 4, and 5 are counted as ‘No’. The C-SSRS is designed to ask item 3, 4, and 5 to subjects only when item 2 is ‘Yes’.

C-SSRS will be listed.

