Body temperature, blood pressure, pulse rate		X	X ^{d)}	X	X	X	X ^{e)}	X	X	X	X	X	X	X	X	X	X	X	X	X	X	X	
Adverse event monitoring			←																			→	
Blood sampling for PK					X		X ^{e)}			X							X			X	X		
Questionnaire																				X	X		

- a) Tab-Day 1 is defined as the day of the initial administration of DSP-5423 (tablet), and Day 1 is defined as the day of the initial application of DSP-5423P.
- b) At Visit 2 (before administration initiation of DSP-5423 (tablet)), Visit 6 (the end of DSP-5423 (tablet) treatment phase) and Visit 113 (the end of DSP-5423P treatment phase), blood samples will be collected under fasting conditions (at least 10 hours after the last meal). At other visits, blood samples should be collected under fasting conditions (at least 10 hours after the last meal) whenever possible.
- c) To be performed only in female subjects who are premenopausal and of childbearing potential.
- d) Must be performed before the beginning of treatment with DSP-5423 (tablet). For the subject treated with any antipsychotic, must be performed after discontinuation of antipsychotics and before the beginning of treatment with DSP-5423 (tablet).
- e) Must be performed before the beginning of treatment with DSP-5423P.
- f) If the subject discontinues the study drug during the DSP-5423 (tablet) treatment phase, the subject will undergo the following safety assessments: study treatment compliance, DIEPSS, C-SSRS, laboratory test, pregnancy test, 12-lead ECG, body weight, body temperature, blood pressure, pulse rate, and adverse event monitoring at the discontinuation visit.
- g) Must be performed before the initiation of post-treatment with antipsychotics excluding the study drug.

Table 3 Schedule of Assessments (Cohort 2)

		DSP-5423P treatment phase (52 weeks)															Discontinuation	Follow-up phase (1-2 weeks)	
Visit No.	-	1	2	101	102	103	104	105	106	107	108	109	110	111	112	113			
Timeline from initiation of DSP-5423P application	-	Screening	Baseline	Week 1	Week 2	Week 4	Week 6	Week 8	Week 12	Week 16	Week 20	Week 24	Week 28	Week 36	Week 44	Week 52			
Visit window (Day)		-28-	-2-1	5-11	12-18	26-32	40-46	54-60	78-92	106-120	134-148	162-176	190-204	239-267	295-323	351-379	At discontinuation +5	6~17 days after completion of treatment or discontinuation	
Obtaining informed consent	X																		
Patient demographics and medical history	X																		
Dispense study drug		X ^{a)}	X	X	X	X	X	X	X	X	X	X	X	X	X				

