7.2.1 Adverse event

In this study, relevant events occurred from the treatment initiation of DSP-5423 (tablet) to follow-up visit in cohort 1 and ones occurred from the initiation of DSP-5423P application to follow-up visit in cohort 2 will be captured as adverse events. An AE can, therefore, be any unfavorable and unintended sign (including an abnormal laboratory finding), symptom, or disease occurring after the administration of a medicinal (investigational) product, whether or not considered related to the medicinal (investigational) product.

In the cohort 1, AEs that occur during the DSP-5423 (tablet) treatment period and worsen during the DSP-5423P application period will be recorded as both AEs in the DSP-5423 (tablet) administration period and also as AEs in the DSP-5423P application period with start date as the onset date of the worsening AE. AEs that occur during the DSP-5423 (tablet) treatment period without further worsening in the DSP-5423P application period will be recorded as AEs only in the DSP-5423 (tablet) treatment period

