8.4 Baseline

Baseline value for analysis (for the DSP-5423P treatment period) is defined as the last non-missing data on or prior to Day 1.

Regarding to Cohort 1, baseline value for the DSP-5423 (tablet) administration period (Tab-Baseline) is defined as the last non-missing data on or prior to the day of initial administration of DSP-5423(tablet).

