9.12.1 Adverse event

The adverse event will be coded using the Medical Dictionary for Regulatory Activities (MedDRA), Version 19.1. Treatment-emergent adverse event (TEAE) is defined as adverse events with start date on or after Day 1. Regardless of cohort, adverse events occurred on same date as the initial date of application of DSP-5423P will be defined as TEAE. All adverse events, regardless of TEAE or not, will be listed. A treatment-related TEAE is defined as a TEAE for which the causal relationship to the study treatment is either ‘definite’, ‘probable’, or ‘possible’.

The summary of TEAE will include the number of event, and the number and percentage of subjects which are classified in the following TEAE or treatment-related TEAE categories. Extrapyramidal (EPS) adverse event will be defined based on MedDRA PT and determined at blinded data review meeting. The skin-related adverse event will be defined as an adverse event

with any application sites collected on EDC.

- Adverse event (any TEAE)
- Death (TEAE leading to death)
- Serious adverse event (serious TEAE)
- Adverse event leading to treatment discontinuation
 - (TEAE leading to treatment discontinuation)
- Severe adverse event (severe TEAE)
- Extrapyramidal adverse event (extrapyramidal TEAE)
- Skin-related adverse event at the application site (skin related TEAE)

The number and percentage of subjects who have TEAE or treatment-related TEAE will be summarized by SOC/PT for each cohort. If a subject has multiple events categorized in same SOC/PT, the subject will be counted only one time into the SOC/PT. SOCs are sorted by alphabetically and PTs are sorted within SOC in descending order of frequency of cohort total. If there are ties, PTs are sorted by alphabetically. TEAE leading to treatment discontinuation will be summarized in the same manner.

Common TEAE are PT of TEAEs experienced by 2% or more subjects in cohort total. Common TEAE and common treatment-related TEAE will be summarized by SOC/PT.

The number and percentage of subjects who have TEAE or treatment-related TEAE will be summarized by SOC/PT and maximum severity. For this summaries, if a subject experienced more than one episode of a TEAE within a PT, the subject is counted only once in the PT at the maximum severity. If the maximum severity is missing, the episode will be kept as missing (not specified). In determining maximum severity, severities are ranked from missing (not specified), mild, moderate, to severe.

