9.12.5 DIEPSS

Observed values and changes from baseline in DSP-5423P application period in DIEPSS total score excluding overall severity and item scores will be summarized by visits (including LOCF endpoint). The overtime change from baseline of DSP-5423P application period in DIEPSS total score excluding overall severity will be plotted for each cohort with +/-SD.

For DSP-5423(tablet) treatment period in Cohort 1, observed value and change from baseline in DSP-5423(tablet) treatment period in DIEPSS total score excluding overall severity and item scores will be summarized by visits. For both DSP-5423(tablet) and DSP-5423P periods in Cohort 1, the overtime change from baseline of DSP-5423(tablet) treatment period in DIEPSS total score excluding overall severity will be plotted with +/-SD.

DIEPSS total score and item scores will be listed.

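### Table 14.3.8.4 measures cohort 1 patch-phase emergence of suicidality only from the pre-tablet baseline, and the tablet-period C-SSRS rows omit subjects who never applied a patch

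*SAP*

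**What the plan says.** **Baseline.** For C-SSRS, SAP 9.12.6 states that "baseline for Cohort 1 is defined as baseline at DSP-5423(tablet) treatment period"; cohort 2 takes the baseline of its patch period. Emergence of ideation, serious ideation, behavior and any suicidality is then looked for only after baseline in the patch period. Subjects positive at the chosen baseline leave the denominator. SAP 10.2 lists the result as Table 14.3.8.4, titled for the DSP-5423P treatment phase.

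The general rule in SAP 8.4 is different: "Baseline value for analysis (for the DSP-5423P treatment period) is defined as the last non-missing data on or prior to Day 1". For cohort 1, 8.4 adds that the "baseline value for the DSP-5423 (tablet) administration period (Tab-Baseline) is defined as the last non-missing data" up to the first tablet day. Protocol Table 2 schedules a C-SSRS at Visit 6, and footnote e says of it: "Must be performed before the beginning of treatment with DSP-5423P".

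**Cohort total.** SAP 9.12 restricts C-SSRS summaries to the individual cohorts. SAP 9.12.6 asks for each cohort and a total.

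**Population.** SAP 9.12.6 also asks for rows at each visit and for the whole tablet period. SAP 10.2 places Tables 14.3.8.1 to 14.3.8.3 on the Safety Population, which SAP 6.1 defines by at least one patch application. The tablet-phase tables for adverse events, laboratory data, vital signs, ECG and DIEPSS are instead placed on subjects treated with the tablet.

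**The concern.** The primary objective is the safety of the patch, a secondary objective is the safety of switching from tablet to patch, and C-SSRS is a listed safety endpoint. A reader of a patch-phase emergence table will take it to show what arose after the patch began. For cohort 1 it shows what was absent before the tablet and present at some time on patch, with six weeks of tablet treatment in between. It cannot separate suicidality present at the switch from suicidality that appeared after it.

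Elsewhere the SAP anchors patch-phase safety at the switch. For adverse events, "Treatment-emergent adverse event (TEAE) is defined as adverse events with start date on or after Day 1", and a tablet-onset event "without further worsening in the DSP-5423P application period will be recorded as AEs only in the DSP-5423 (tablet) treatment period". For DIEPSS, SAP 9.12.5 provides both views: "Observed values and changes from baseline in DSP-5423P application period in DIEPSS total score" are tabulated by visit, and for the whole of cohort 1 "the overtime change from baseline of DSP-5423(tablet) treatment period in DIEPSS total score excluding overall severity will be plotted". C-SSRS emergence gets only the pre-tablet view.

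The tablet-period C-SSRS rows describe only subjects who went on to the patch. Protocol 13.1 lists suicide ideation among the possible reasons for termination, so the omitted group may differ on the very outcome being tabulated.

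**Working it through.** The plan gives no figure to reproduce, so the check traces definitions and then sizes the effect of one subject.

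**Step 1: classify every pattern.** Write each cohort 1 subject as (pre-tablet, Visit 6, any patch visit), with N for absent and Y for present. The 9.12.6 denominator is pre-tablet N. The 8.4 denominator is Visit 6 N, taking Visit 6 as the last value on or before Day 1. Three of the emergence definitions in 9.12.6 are awkwardly worded. I read all four as absent at baseline and present on patch, which is how the any-suicidality definition is written.

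| Pattern | SAP 9.12.6 baseline | SAP 8.4 Day-1 baseline |
|---|---|---|
| N-N-N | non-case | non-case |
| N-N-Y | emergent | emergent |
| N-Y-N | non-case | excluded |
| N-Y-Y | emergent | excluded |
| Y-N-N | excluded | non-case |
| Y-N-Y | excluded | emergent |
| Y-Y-N | excluded | excluded |
| Y-Y-Y | excluded | excluded |

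Four of the eight patterns change class. Two change the numerator: N-Y-Y (onset on tablet, persists) and Y-N-Y (absent at the switch, recurs on patch). The other two change only the denominator. Protocol Table 2 has four C-SSRS assessments between the pre-tablet baseline and the first patch (Visits 3, 4, 5 and 6), so on-tablet onset can be observed.

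**Step 2: effect of one subject.** Let k be the emergent cases and D the denominator under 9.12.6. Moving one subject to the Day-1 baseline changes k/D as follows:

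- N-Y-Y: (k − 1)/(D − 1)
- Y-N-Y: (k + 1)/(D + 1)
- N-Y-N: k/(D − 1)
- Y-N-N: k/(D + 1)

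Assumptions: k = 1 to 5 is assumed. D = 50 to 100 is anchored on Protocol 15.1: 50 is the target number with 6 or more weeks on patch in cohort 1, and 100 is about half of the 200 enrolled. Neither is the true denominator, which also includes shorter patch exposure and drops baseline-positive subjects.

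| Pattern | k = 2, D = 50 (2/50 = 4.00%) | k = 2, D = 100 (2/100 = 2.00%) | Change over k = 1–5, D = 50–100 (points) |
|---|---|---|---|
| N-Y-Y | 1/49 = 2.04% (−1.96) | 1/99 = 1.01% (−0.99) | −0.96 to −2.00 |
| Y-N-Y | 3/51 = 5.88% (+1.88) | 3/101 = 2.97% (+0.97) | +0.94 to +1.92 |
| N-Y-N | 2/49 = 4.08% (+0.08) | 2/99 = 2.02% (+0.02) | +0.01 to +0.20 |
| Y-N-N | 2/51 = 3.92% (−0.08) | 2/101 = 1.98% (−0.02) | −0.01 to −0.20 |

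The two numerator patterns can also cancel. Take 50 subjects: 2 Y at both baselines, 2 N-N-Y, 2 N-Y-Y and 2 Y-N-Y (assumed), the rest N-N-N. Both baselines then give 4/46 = 8.7%, but two of the four cases are different people.

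**Step 3: who is missing from the tablet rows.** Anyone who took tablet and applied no patch is outside the Safety Population. That covers those who stopped on tablet, for whom Protocol 13.2 requires a C-SSRS, and those who completed tablet without switching, a disposition category in SAP 9.1. Their number is not given. If 50 reach the patch and tablet-phase loss is assumed at 10%, 20% or 30%, starters number 50/0.9 ≈ 56, 50/0.8 ≈ 63 or 50/0.7 ≈ 72, and the rows omit 6, 13 or 22.

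**The case against.** The strongest reply is that this is a prespecified, endpoint-specific choice. A specific definition governs over the general rule in 8.4. SAP 9.4 and 9.5 also describe cohort 1 at its tablet-period baseline, and asking whether suicidality arose since before any study blonanserin is a sensible question. That stands: the pre-tablet analysis is worth keeping, and the objection here is to its being the only one in a patch-phase table. A reader might infer that it breaches the protocol. The documents do not support that firmly, because the protocol's only C-SSRS summary (15.3.6.5) uses no baseline and emergence is a SAP addition.

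Much of the information is also planned elsewhere. Tables 14.3.8.1 to 14.3.8.3 show each visit, including Visit 6, and the C-SSRS listings cover all patients. That limits the harm, but visit-level counts do not show who changed state, and listings are not a summary.

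Three further inferences go too far:

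- That the AE and C-SSRS tables will contradict each other on the same subject. This requires the ideation also to be recorded as an AE. AEs are elicited by non-leading questions, C-SSRS is a structured rating, and no text says that a positive item becomes an AE.
- That the population restriction is hidden. The Safety Population label, SAP 6.1 and the opening rule of SAP 9 disclose it. What remains is that it differs from the sibling tablet-phase tables.
- That leaving C-SSRS out of the tablet discontinuation mapping in SAP 8.5 loses data from the planned tables. Subjects who stop on tablet are not in those tables, so the gap matters only once the population is changed.

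**Conclusion.** The point holds and should be fixed, within narrow limits. Table 14.3.8.4 as specified does not isolate suicidality arising after the switch in cohort 1. It can err in either direction, and excluding recurrence on patch is the less visible of the two errors. A cohort total would pool a pre-tablet with a pre-patch reference, and the SAP contradicts itself on whether to show one. The tablet-period C-SSRS rows are conditional on reaching the patch, unlike the other tablet-phase safety tables.

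The size is about 1 to 2 percentage points per reclassified subject under the assumed k and D. A reader might take this for an expected bias. It is not one: the documents give no frequency of either pattern. Exclusion criterion 7 and termination for suicide ideation both suggest few cases. The effect is confined to descriptive summary tables; the protocol 15.3.6.5 summary does not depend on baseline, and nobody is lost from the all-patient listings.

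**What to change.** - **(a) Emergence.** Base Table 14.3.8.4 on the Section 8.4 Day-1 baseline in both cohorts. Keep the pre-tablet version for cohort 1 as a companion table with its baseline in the title, so that suicidality first arising on either formulation stays visible. While editing, correct the wording of the emergence definitions.
- **(b) Tablet period.** Report tablet-period C-SSRS in separate tables on all subjects treated with DSP-5423 (tablet), as SAP 10.2 already does for DIEPSS. Then add C-SSRS to the tablet discontinuation mapping in 8.5.
- **(c) Cohort total.** Make 9.12 and 9.12.6 agree, and show no emergence total that pools pre-tablet and pre-patch baselines.

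The cost is a few extra descriptive tables, one mapping entry and SAP wording. It is more than one table, because (b) splits the tablet and patch rows. No new data are needed: the schedule already collects C-SSRS at Visit 6 and at discontinuation on tablet.

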15.1 Target sample size

Number of subjects enrolled: 200 subjects

- Number of subjects treated with DSP-5423P for 6 weeks and more in cohort 1: 50 subjects
- Number of subjects treated with DSP-5423P for 52 weeks in either cohort 1 or cohort 2: 100 subjects

The new enrollment can be terminated at the time when 100 subjects with 52-week exposure of DSP-5423P are collected, together with a separate confirmatory study [Confirmatory Study of DSP-5423P in Patients with Schizophrenia <Phase 3> (protocol: D4904020)].

Rationale

Based on the guideline, THE EXTENT OF POPULATION EXPOSURE TO ASSESS CLINICAL SAFETY FOR DRUGS INTENDED FOR LONG-TERM TREATMENT OF NON-LIFE-THREATENING CONDITIONS dated 24 May 1995, 100 subjects with one year (52 weeks) exposure of DSP-5423P will be collected in cohort 1 and 2. In addition, to investigate the safety and efficacy of switching DSP-5423 (tablet) to DSP-5423P, approximately half of the target number of subjects will be enrolled in cohort 1 as subjects who switched DSP-5423 (tablet) to DSP-5423P. Considering approximately half of enrolled subjects early terminated in previous studies of DSP-5423 (tablet),

target number of subjects was set to 200. No statistical consideration was applied.

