15.3.6.5 C-SSRS

The number and percentage of subjects with either suicidal ideation or suicidal behavior at least once in DSP-5423P application period will be summarized.

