4.2 Secondary objective

- To evaluate the safety and effectiveness of switching from DSP-5423 (tablet) to DSP-5423P.
- To evaluate the effectiveness and pharmacokinetics of DSP-5423P (40-80 mg/day) for 52-week treatment.

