4.3 Overall study design of clinical study

This clinical study is a multicenter, perform uncontrolled, open-label, long-term administration study consisting of two cohorts. The study schematics of clinical study are presented in Figures 1 (cohort 1) and 2 (cohort 2). Details of the study assessment and other procedures (assessment, observation, laboratory test) to be performed are presented in Tables 2 (cohort 1), 3 (cohort 2) and Chapter 11 in the protocol. In both cohorts, Day 1 is defined as the day of the initial application of DSP-5423P.

Cohort 1, consisting of DSP-5423 (tablet) treatment period and DSP-5423P treatment period, and cohort 2, consisting only of DSP-5423P treatment period, will be conducted in different subjects,

and cohort 2 will be initiated after enrollment in cohort 1 has been completed. Enrollment in cohort 1 will be terminated when the number of total subjects whose DSP-5423P treatment duration is 6 weeks or more reached 50. At the completion of enrollment in cohort 1 and at the initiation of enrollment in cohort 2, the sponsor will notify the participating study centers of that.

4.3.1 Cohort 1

Cohort 1 consists of 3 periods: DSP-5423 (tablet) treatment period (6 weeks), DSP-5423P treatment period (52 weeks) and follow-up period (1-2 weeks). Prior to initiation of DSP-5423 (tablet) treatment period, washout period (up to 4 weeks) will be arranged according to the dose of prior antipsychotics (haloperidol equivalent).

[figure not shown]
1) DSP-5423 (tablet) treatment period

DSP-5423 (tablets) will be administered orally twice daily after breakfast and evening meal for 6 weeks. The initial dose of DSP-5423 (tablet) will be 8mg/day. DSP-5423 (tablet) will be administered as flexible dose (8, 12, 16 mg/day) according to the dose adjustment criteria.

2) DSP-5423P treatment period

DSP-5423P will be applied once daily for 52 weeks. The study drug will be applied to the subject's back, chest, or abdomen. Start DSP-5423P application with the dosage according to the final dosage of DSP-5423. DSP-5423P will be applied as flexible dose (40, 60, 80 mg/day) according to the dose adjustment criteria.

Figure 1 Study schematic (cohort 1)

* If the dose of the prior antipsychotics is 12.0 mg/day or less (haloperidol equivalent), to initiate the administration of the DSP-5423 (tablet) after termination of the prior antipsychotics. Washout period may be arranged and down-titration would be done as needed prior to termination.

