6.1 Safety analysis population

Subjects with at least one application of DSP-5423P.

Efficacy analysis will also be performed based on the safety analysis population.

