8.5 Analysis Visit

Data of DSP-5423P treatment period is defined as the data captured on Day 1 through 7 days after the final application of DSP-5423P.

All data will be organized and analyzed according to the scheduled timing as outlined in Tables 1 and 2 Schedule of Assessments and according to the visit denoted in the CRFs. Unscheduled visits may not be used for any analysis unless otherwise specified. However, the data collected at the discontinuation visit within 7 days from the final application of study drug are mapped to the next scheduled visit of the actual discontinuation date. In listing, all data including unscheduled visit data should be presented.

1) CRF discontinuation visits in DSP-5423 (tablet) treatment period

Assessments and tests	Relative Day	Analysis Visit
PANSS, CGI-S, DIEPSS, body weight, body temperature, blood pressure, pulse rate	Tab-Day 1 to 11	Tab-W1, 2, 4, 6
	Tab-Day 12 to 18	Tab-W2, 4, 6
	Tab-Day 19 to 32	Tab-W4, 6
	Tab-Day 33 or later	Tab-W6
Laboratory test, ECG	Tab-Day 1 to 18	Tab-W2, 6
	Tab-Day 18 or later	Tab-W 6

The Tab-Day 1 is defined as the date of initial administration of DSP-5423 (tablet). CRF discontinuation visits in DSP-5423 (tablet) treatment period is defined as data on first non-missing (ex. no visit or results are missing) visit which meets all above requirements. Laboratory test and vital sign (body temperature, blood pressure, pulse rate) are performed visit handling for each item. Others are not considered as missing if they have any one component.

2) CRF discontinuation visits in DSP-5423P application period

Assessments and tests	Relative Day	Analysis Visit
PANSS, CGI-S, DIEPSS, C-SSRS,	Day 1 to 11	W1, 2, 4, 6, 8, 12, 16, 20, 24, 28, 36, 44, 52
	Day 12 to 18	W2, 4, 6, 8, 12, 16, 20, 24, 28, 36, 44, 52

Assessments and tests	Relative Day	Analysis Visit
Skin irritation assessment, body weight, body temperature, blood pressure, pulse rate	Day 19 to 32	W4, 6, 8, 12, 16, 20, 24, 28, 36, 44, 52
	Day 33 to 46	W6, 8, 12, 16, 20, 24, 28, 36, 44, 52
	Day 47 to 60	W8, 12, 16, 20, 24, 28, 36, 44, 52
	Day 61 to 92	W12, 16, 20, 24, 28, 36, 44, 52
	Day 93 to 120	W16, 20, 24, 28, 36, 44, 52
	Day 121 to 148	W20, 24, 28, 36, 44, 52
	Day 149 to 176	W24, 28, 36, 44, 52
	Day 177 to 204	W28, 36, 44, 52
	Day 205 to 267	W36, 44, 52
	Day 268 to 323	W44, 52
	Day 324 or later	W52
Laboratory test, ECG	Day 1 to 18	W2, 6, 12, 20, 28, 36, 44, 52
	Day 19 to 46	W6, 12, 20, 28, 36, 44, 52
	Day 47 to 92	W12, 20, 28, 36, 44, 52

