The number and percentage of subjects who have TEAE or treatment-related TEAE will be summarized by SOC/PT and first onset date. If a subject experienced more than one event within a PT, the subject is counted only once in the PT based on the earliest event started on the same or closer to Day 1. Denominator of percentage for each period of interest is the number of subjects who were treated with DSP-5423P in each period.

Onset: Day 1 to 7, Day 8 to 14, Day 15 to 28, Day 29 to 42; Week 1 to 6;
Week 1 to 13; Week 14 to 26; Week 27 to 39; Week 40 or later
(Week 1=Day 1 to 7, Week 2=Day 8 to 14)

As TEAE of interests, Extrapyramidal TEAE and skin related TEAE will be summarized by SOC/PT. Additionally, those TEAE will be summarized by maximum severity or first onset date in same manner as summaries of TEAE. In summary tables, the frequencies for entire TEAE related to extrapyramidal symptoms or TEAE related to skin, not just by SOC/PT, will be presented.

Adverse events and extrapyramidal adverse events started during DSP-5423(tablet) treatment period of Cohort 1, meaning Tab-Day 1 to Day -1 will be summarized by SOC/PT.

Listings for adverse events, AE leading to death, SAE, AE leading to treatment discontinuation, Extrapiramidal AE and skin related AE will be generated. Both TEAE and pre-treatment event which started before Day 1, will be included in those listings. In the listing for skin related AE, the application site will also be presented.

The adverse events during DSP-5423(tablet) treatment period of Cohort 1 will be listed.

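### For Cohort 1, SAP 9.12.6 sets no six-week cumulative patch window for C-SSRS, so the whole-tablet-period and whole-patch-period percentages are not comparable

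*SAP*

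**What the plan says.** SAP 9.12.6 (C-SSRS) uses the same set of windows for ideation, behaviour and any suicidality. For the last of these the wording is "with no suicidality will be summarized at baseline, each visit, entire DSP-5423(tablet) treatment period, and entire DSP-5423P application period". The only cumulative windows are thus the two whole periods. The results go into Tables 14.3.8.1 to 14.3.8.3, which SAP 10.2 assigns to the Safety Population, defined in SAP 6.1 as "Subjects with at least one application of DSP-5423P".

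SAP 4.3 gives the Cohort 1 periods as 6 weeks on tablet and 52 weeks on patch. The Cohort 1 schedule (SAP 4.4, Table 1) marks C-SSRS after tablet baseline at Visits 3 to 6 (Tab-Weeks 1, 2, 4, 6) and on patch at Visits 101 to 113. The patch visits in SAP 8.5 are "W1, 2, 4, 6, 8, 12, 16, 20, 24, 28, 36, 44, 52".

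Two other passages bear on the point. A secondary objective in SAP 4.2 is "To evaluate the safety and effectiveness of switching from DSP-5423 (tablet) to DSP-5423P". For first onset of adverse events, SAP 9.12.1 does include a six-week patch window: "Onset: Day 1 to 7, Day 8 to 14, Day 15 to 28, Day 29 to 42; Week 1 to 6". Nothing equivalent appears in SAP 9.12.6, nor does an exposure-adjusted or per-rating rate.

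**The concern.** The percentage of subjects positive at least once cannot fall, and will usually rise, as more ratings are taken on the same people. When one window has about three times the ratings and almost nine times the weeks of the other, the longer one tends to show the larger percentage even if nothing about the subject's risk has changed.

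Switching safety is a stated objective, and C-SSRS is a listed safety endpoint. Someone looking for the effect of the switch on suicidality will naturally set the two Cohort 1 period figures against each other. As planned, that reading cannot separate a change after the switch from longer observation.

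The visit rows do not supply the missing figure. Suppose, purely as illustration, that one subject is positive at each of Weeks 1, 2, 4 and 6. The number of distinct subjects positive over six weeks could then be anything from 1 (the same person four times) to 4. Only the subject listings would settle it.

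**Working it through.** **Plan's own figure.** Protocol 15.1 targets 100 subjects with 52 weeks of exposure and expects about half to terminate early: 100 / (1 − 0.5) = 200, the stated enrolment. The documents give no suicidality rate and no tablet-to-patch ratio, so there is nothing further to reproduce.

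**Windows (SAP 4.3, 4.4, 8.5).** Ratings: 13 / 4 = 3.25. Time: 52 / 6 = 8.67.

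**Assumptions.** The rating probability p, the within-subject correlation ρ and the hazard are all assumed. Dropout is assumed exponential, reaching 50% at patch week 52, with the discontinuation rating counted. This gives on average 10.7 ratings and 37.5 weeks on patch. The tablet row is taken as complete. Underlying risk is the same in both periods throughout.

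**(a) Independent ratings.** P(at least one) = 1 − (1 − p)^n, with n = 4 or 13.

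| p per rating | Tablet | Patch, no dropout | Ratio | Patch, 50% dropout | Ratio |
|---|---|---|---|---|---|
| 0.5% | 2.0% | 6.3% | 3.18 | 5.2% | 2.64 |
| 1% | 3.9% | 12.2% | 3.11 | 10.2% | 2.59 |
| 2% | 7.8% | 23.1% | 2.98 | 19.3% | 2.49 |
| 5% | 18.5% | 48.7% | 2.62 | 41.5% | 2.24 |

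**(b) Correlated ratings (beta-binomial).** With a = p(1 − ρ)/ρ and b = (1 − p)(1 − ρ)/ρ, P(at least one) = 1 − B(a, b + n)/B(a, b). The percentages are for p = 1%; the last column gives the range over p = 0.5% to 5%.

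| ρ | Tablet | Patch, no dropout | Ratio | Patch, 50% dropout | Ratio | Ratio with dropout, all p |
|---|---|---|---|---|---|---|
| 0.1 | 3.42% | 8.04% | 2.35 | 6.95% | 2.03 | 1.87–2.05 |
| 0.3 | 2.65% | 4.75% | 1.79 | 4.26% | 1.61 | 1.55–1.62 |
| 0.5 | 2.07% | 3.14% | 1.52 | 2.89% | 1.40 | 1.37–1.40 |
| 0.7 | 1.59% | 2.09% | 1.31 | 1.98% | 1.24 | 1.23–1.24 |
| 0.9 | 1.19% | 1.32% | 1.12 | 1.29% | 1.09 | 1.08–1.09 |

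**(c) New-onset events at a constant hazard.** For six-week risk r, h = −ln(1 − r)/6. The 52-week risk is 1 − exp(−52h) without dropout. With dropout at rate λ = ln 2 / 52 it is h/(h + λ) × [1 − exp(−52(h + λ))].

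| r | Patch, no dropout | Ratio | Patch, 50% dropout | Ratio |
|---|---|---|---|---|
| 1% | 8.3% | 8.34 | 6.1% | 6.05 |
| 2% | 16.1% | 8.03 | 11.7% | 5.85 |
| 5% | 35.9% | 7.18 | 26.6% | 5.31 |
| 10% | 59.9% | 5.99 | 45.4% | 4.54 |

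**After cutting the patch window to Weeks 1-6.** There are 4 ratings against 4 and 6 weeks against 6. The ratio is 1.00 without dropout and 0.96 to 1.00 with it, across all three models.

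**The case against.** The strongest reply is that the plan prescribes no such comparison. Protocol 15.3.6.5 asks only for the patch-period figure: "The number and percentage of subjects with either suicidal ideation or suicidal behavior at least once in DSP-5423P application period will be summarized". The emergence-of-suicidality categories are also confined to the patch period, the study is uncontrolled, and the SAP names no tablet-versus-patch C-SSRS contrast or test. The period lengths are stated openly. This stands, and it limits the point to how a descriptive table is read.

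Four stronger readings that a reader might infer are not supported:

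- *The patch will show several times more suicidality.* No rate or correlation is given in the documents. A multiple of that size needs nearly independent ratings or a constant hazard of new events. The tables count any positive rating, including ideation that persists, and repeat reporters pull the ratio towards 1.
- *There is no matched window at all.* Visit rows exist on both sides at Weeks 1, 2, 4 and 6. Only the cumulative one is missing.
- *These are the only pooled tablet and patch suicidality figures.* Tablet-period adverse events are tabulated by SOC and PT (Table 14.3.1.21), and patch events by first onset have a six-week window (Table 14.3.1.6). A suicidal event recorded as an adverse event can be compared there, although that need not cover every positive C-SSRS rating.
- *Equal windows would isolate a switch effect.* Tablet always precedes patch. Tablet Weeks 1-6 follow the stopping of any prior antipsychotic, while patch Weeks 1-6 follow six weeks on tablet. Subjects who stopped before any patch application are outside the Safety Population, so they are missing from the tablet row and their absence may lower it.

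**Conclusion.** The point holds in its limited form. SAP 9.12.6 gives Cohort 1 two cumulative C-SSRS percentages that differ in length and number of ratings, and no matched cumulative patch figure. At equal underlying risk the patch percentage was higher under every model tried. The direction follows from the design; the size rests entirely on assumed rates, correlation and dropout, and spans about 1.1 to 8.3 fold. The low end applies if the same subjects report ideation repeatedly (ρ of 0.3 to 0.9 with 50% dropout), and the high end to new-onset events at a constant hazard without dropout. No planned test or formal estimate is affected. It is a worthwhile, inexpensive improvement to a descriptive safety table that serves a stated secondary objective.

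**What to change.** In SAP 9.12.6, add a cumulative row *DSP-5423P Weeks 1-6* to Tables 14.3.8.1 to 14.3.8.3. Build it from Visits 101 to 104 plus discontinuation ratings mapped to those visits under SAP 8.5. Naming the visits also keeps the Visit 6 rating, taken before the first patch, in the tablet row. For Cohort 1, read the new row against the tablet-period row in the same subjects. The nominal weeks match; the last visit window differs slightly (Tab-Day 40 to 43 against Day 40 to 46).

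Keep the 52-week row as a stand-alone result and add three footnotes: it is not comparable in length with the tablet period; the tablet row excludes subjects who stopped before any patch application; and the tablet-then-patch order is fixed, so matching removes the length artefact without isolating an effect of switching.

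The cost is one extra row and the footnotes in three tables, with no new data.
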